### **5.5.3.3 Handling of non-study treatment**

The following non-study treatment has to be monitored specifically and recorded in the CRF:

- ACEi/ARB treatment prior to randomization and/or after early discontinuation of study treatment.
- All protocol required background therapy.
- Rescue treatment.

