**4. Stopping Study Treatment**

If needed, the study treatment may be stopped completely, however, the patient should continue to attend all study visits and be followed until the completion of the study. See [Section 5.5.6](#).

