### 5.5.6 Rescue medication for worsening heart failure

At any time during the 12 week randomized, double-blind treatment epoch, investigators have the option to withdraw patients from study treatment if they develop signs and symptoms of worsening heart failure for which the investigator would like to administer appropriate therapy.

- Appropriate adjustments, intensifications, or additions to concomitant medications should be considered before deciding to withdraw the patient from study treatment.
- **Other than their study treatment, patients CANNOT receive ACEis, ARBs, or sacubitril/valsartan during the study. These medications can ONLY be administered if the investigator believes that the patient needs to be withdrawn from study treatment so that they may be treated with these therapies due to signs and symptoms of worsening heart failure.**
- **A 36 hour wash-out period is required if the investigator chooses to withdraw the patient from double-blind treatment and switch to sacubitril/valsartan or ACEi due to symptoms of worsening heart failure.**

- Use of rescue medication must be recorded on the Concomitant medications eCRF.

Investigators will use clinical judgement to determine if patient condition requires closer monitoring. Unscheduled visits are permitted as needed.

Guidance on handling hyperkalemia, hypotension, and renal dysfunction are provided to investigators in the appendices.

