### **5.6.2 Discontinuation of study treatment**

Discontinuation of study treatment for a patient occurs when study drug is stopped earlier than the protocol planned duration, and can be initiated by either the patient or the investigator.

The investigator must discontinue study treatment for a given patient if, on balance, he/she believes that continuation would negatively impact the risk/benefit of trial participation.

Patients may voluntarily discontinue the study drug for any reason at any time.

Study treatment must be discontinued under the following circumstances:

- Patient wish
- Withdrawal of consent
- Pregnancy (see [Section 6.5.8](#) and [Section 7.6](#))
- Use of prohibited treatment as per recommendations in [Table 5-9](#)
- Any protocol deviation that constitutes a risk to the patient

- Any situation in which study participation might result in a safety risk to the patient
- Unresolved worsening HF

Study medication may be discontinued at the investigator's discretion if any of the following serious suspected drug-related AEs occur:

- Symptomatic hypotension
- Suspected occurrence of angioedema. A patient with any signs or symptoms of clinically significant angioedema should be thoroughly evaluated by the investigator to determine if it constitutes a reason for discontinuation of study medication.
- Any laboratory abnormalities that in the judgment of the investigator, taking into consideration the subject's overall status, prevents the subject from continuing participation in the study.

Depending on the serum potassium, blood pressure, or eGFR, patients may need to have their study drug dose or the dose of another concomitant medication reduced or discontinued; or, if appropriate, have potentially contributing agents adjusted. Refer to appendices for treatment guidelines for hyperkalemia, hypotension or renal dysfunction, respectively.

If discontinuation of study treatment occurs, the patient should NOT be considered withdrawn from the study. The investigator must determine the primary reason for the patient's premature discontinuation of study treatment and record this information on End of Study Treatment eCRF. After study treatment discontinuation, the patient should attend the regularly scheduled visits and have all study assessments performed.

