#### **5.6.4 Loss to follow-up**

For patients whose status is unclear, because they fail to appear for study visits without stating an intention to withdraw, the investigator should show "due diligence" by contacting the patient, family or family physician as agreed in the informed consent and by documenting, in the source documents, steps taken to contact the patient, e.g. dates of telephone calls, registered letters, etc. A patient should not be formally considered lost to follow-up until his/her scheduled end of study visit would have occurred.

For subjects whose status is unclear because they fail to appear for study visits without stating an intention to discontinue or withdraw, the investigator should show "due diligence" by documenting in the source documents steps taken to contact the subject, e.g. dates of telephone calls, registered letters, etc. A patient cannot be considered as lost to follow-up until the time point of his/her scheduled end of study visit has passed.

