2.1.1 General definitions

Study treatment

Patients will receive either sacubitril/valsartan or enalapril during the first 12 weeks of the study. Study treatment will refer to either of these two drugs.

Baseline

In general, baseline is defined as the last non-missing assessment prior to or on the start date of study treatment (randomization date for patients not treated). For hemodynamic variables baseline is defined as the assessment with a planned time point value of 'Visit_1_Baseline'.

Unscheduled assessments will be excluded from the determination of baseline.

Date of first administration of study treatment

Double-blind phase: The date of first administration of study treatment in the double-blind phase is defined as the first date a dose of study treatment is administered and recorded on the Dosage Administration Record - At Visit (Visit 2) electronic case report form (eCRF).

Open-label phase: The date of first administration of study treatment in the open-label phase is defined as the first date a dose of sacubitril/valsartan is administered in the open-label phase and recorded on the Dosage Administration Record - At Visit (Visit 7) eCRF.

Date of last administration of study treatment

Double-blind phase: The date of last administration of study treatment in the double-blind phase is defined as the last date a dose of study treatment is administered in the double-blind phase and recorded on the Dosage Administration Record - At Visit (Visit 6) eCRF. In the event this date is not available from the Dosage Administration Record - At Visit (Visit 6) eCRF, it will

be determined from the End of Study Treatment eCRF or Dosage Administration Record - Summary eCRF.

Open-label phase: The date of last administration of study treatment in the open-label phase is defined as the last date a dose of sacubitril/valsartan is administered in the open-label phase and recorded on the Dosage Administration Record - Summary eCRF.

The date of last administration of study treatment during the study is defined as the last date a dose of study treatment is administered and recorded on the End of Study Treatment eCRF. In the event this date is not available from the End of Study Treatment eCRF, it will be obtained from the Dosage Administration Record - Summary eCRF.

Study day

The study day describes the day of the assessment relative to the date of randomization.

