The study day will be calculated as the difference between the date of assessment and the date of randomization plus 1. If the date of assessment is prior to the date of randomization, the study day will be negative and will be calculated as the difference between the date of the assessment and the date of randomization.

Double-blind phase

Assessments performed at Weeks 1, 2, 4, or 12 (including, but not limited to, vital signs) will be assigned to the double-blind phase for summarization purposes. Unscheduled assessments are not assigned to a study phase for purposes of by-visit summaries.

For summarization of adverse events [AEs], medications, protocol deviations, notable vital signs and laboratory abnormalities, angioedema, and hospitalizations/ED visits/unplanned outpatient clinic visits due to worsening HF symptoms by study phase, an assessment during the double-blind phase is defined as any assessment obtained in the following time interval:

Date of randomization (or date of first administration of study treatment, as appropriate) through the date of the Week 12 visit, inclusive. For patients without a Week 12 visit, a projected Week 12 visit date will be derived relative to their randomization date.

Open-label phase

Assessments performed at Weeks 14 or 24 (including, but not limited to, vital signs) are assigned to the open-label phase for summarization purposes. Unscheduled assessments are not assigned to a study phase for purposes of by-visit summaries.

For summarization of AEs, medications, protocol deviations, notable vital signs and laboratory abnormalities, angioedema, and hospitalizations/ED visits/unplanned outpatient clinic visits due to worsening HF symptoms by study phase, an assessment during the open-label phase is defined as any assessment obtained in the following time interval:

After the date of the Week 12 visit. For patients without a Week 12 visit, a projected Week 12 visit date will be derived relative to their randomization date.

Patients who died, withdrew consent, or were lost to follow-up prior to or on their projected Week 12 visit date will be excluded from the open-label phase.

Last contact

The date of last contact will be determined as the later of the following dates:

- The last visit date for each patient derived by examining all visit data collected in the eCRFs
- Date of discontinuation/study phase completion for the double-blind and open-label phases

Year, month and week

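### The open-label phase in SAP 2.1.1 is set by calendar time with no dose condition, so patients who never took open-label sacubitril/valsartan are counted in its safety tables

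*SAP*

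**What the plan says.** SAP 2.1.1 has two rules for the open-label phase.

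- **Interval rule.** For adverse events, medications, protocol deviations, notable vital signs and laboratory values, angioedema and visits for worsening heart failure, the phase is all time after the Week 12 visit. If there was no such visit, a projected date is used. The only exclusions from the phase are: "Patients who died, withdrew consent, or were lost to follow-up prior to or on their projected Week 12 visit date will be excluded".
- **Visit rule.** "Assessments performed at Weeks 14 or 24 (including, but not limited to, vital signs) are assigned to the open-label phase for summarization purposes".

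Neither rule mentions an open-label dose. SAP 2.8.1.2 (treatment-emergent events), 2.8.2 (deaths, on the FAS) and 2.8.4.3 (angioedema) all tabulate by this phase.

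The protocol retains patients who stop study drug. Under step 4 of 5.5.5, "the patient should continue to attend all study visits and be followed until the completion of the study". Under 5.6.2, "After study treatment discontinuation, the patient should attend the regularly scheduled visits and have all study assessments performed". Such patients may take other therapy. Section 5.5.3.3 has sites record "ACEi/ARB treatment prior to randomization and/or after early discontinuation of study treatment", and 5.5.6 lets the investigator "withdraw the patient from double-blind treatment and switch to sacubitril/valsartan or ACEi" for worsening heart failure.

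**The concern.** A table headed open-label phase will be read as the Week 12–24 safety experience on sacubitril/valsartan, including patients switched from enalapril. As written, it also holds patients who stopped blinded drug, for example enalapril at Week 3, and were followed with no study drug or on an ACEi, an ARB or commercial sacubitril/valsartan.

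The error can go either way. Patients off drug should have fewer drug-related events such as hypotension, which lowers the reported rate. But unresolved worsening heart failure is a mandatory reason to stop study drug (Protocol 5.6.2), so the same patients may have more deaths and heart-failure events, which raises those rates. A reader could not correct for this from the phase percentages.

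**Working it through.** **1. Who is in the phase, as written.** Four rules, taken together:

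- Route into open-label treatment (Protocol 3.1 and 5.5.4): completing 12 weeks of double-blind treatment.
- Follow-up (Protocol 5.5.5 and 5.6.2): continues after drug is stopped.
- Phase membership (SAP 2.1.1): everyone followed past Week 12 unless dead, withdrawn from consent or lost by then.
- Safety Set (SAP 2.2 and 5.6): one dose of double-blind drug is enough. No open-label safety set is defined.

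A patient who stopped blinded drug and stayed in follow-up meets the SAP definition without meeting the protocol's route into open-label treatment. The treatment-emergent window in SAP 2.8.1.2 has no end tied to the last dose, so it does not remove later events. Open-label dose dates are defined in SAP 2.1.1, but in the visible text they feed only the exposure summaries in 2.4.1. Event counts and exposure can therefore cover different patients.

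**2. The plan's own figure.** Protocol Table 5-3 plans about 346 open-label patients. This reproduces from 432 randomized and the 20% dropout in Protocol 9.8: 432 × 0.80 = 345.6. The planned non-entrants number 432 − 346 = 86.

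**3. Size.** Let k be the number of never-dosed patients counted in the phase. The documents do not give it. Assume a share f of the 86 stays in follow-up, so k = 86f.

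- No events among the k patients: the rate is multiplied by 346/(346 + k).
- Illustration with hypotension, using the PARADIGM-HF rates in Protocol 3.6.1 (17.61% sacubitril/valsartan, 11.97% enalapril; a different trial and follow-up period): 17.61% × 346/(346 + k). If the k patients have the enalapril rate instead: (346 × 17.61 + k × 11.97)/(346 + k).
- Deaths or heart-failure events, with risk doubled among the k patients (assumed): the rate is multiplied by (346 + 2k)/(346 + k).

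| f (assumed) | k | Phase denominator | Factor, no events in k | Hypotension, no events in k | Hypotension, enalapril rate in k | Factor, doubled risk in k |
|---|---|---|---|---|---|---|
| 0 | 0 | 346 | 1.00 | 17.6% | 17.6% | 1.00 |
| 0.25 | 22 | 368 | 0.94 | 16.6% | 17.3% | 1.06 |
| 0.5 | 43 | 389 | 0.89 | 15.7% | 17.0% | 1.11 |
| 1 | 86 | 432 | 0.80 | 14.1% | 16.5% | 1.20 |

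**4. Angioedema.** Suppose all k patients took an ACEi at the enalapril rate in Protocol 3.6.1 (10/4229 = 0.24%). The expected misattributed events are then 0, 0.05, 0.10 and 0.20, against 346 × 19/4203 = 1.6 among dosed patients. The effect is small, and SAP 2.8.4.3 already tabulates ACEi and ARB use and lists every event.

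**The case against.** The strongest reply is that the calendar phase is deliberate. The SAP's change history, dated before database lock, records that on-treatment terminology and a 28-day lag were removed and that treatment phase became study phase. A follow-up period suits a protocol that retains patients who stop drug, and deaths by phase on the FAS is ordinary treatment-policy reporting. This stands: the phase definition is not an error. It does not justify presenting the phase without a split by exposure.

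A reader might also infer that the Week 14 and Week 24 columns labelled open-label sacubitril/valsartan (SAP 2.8.3, 2.8.4.1, 2.8.4.2 and 2.12) contain never-dosed patients. The documents do not show this. SAP 2.1.1 assigns those visits to a phase, not to a treatment column. The Safety Set is analysed by treatment received, although that does not cover the biomarker tables, which use the FAS. The wording should be closed off, but misplacement is not established.

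Nor should much rest on exits that the three exclusions do not name, such as physician decision in SAP 2.3.1, or on how losses are dated. Protocol 5.6.4 does say "A patient should not be formally considered lost to follow-up until his/her scheduled end of study visit would have occurred", but the SAP also defines a last-contact date that could be used. This point is secondary.

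Table details sit in a TFL shells document that was not available, and some SAP sections are redacted, including any that describes the heart-failure visit table. These could set a dosed denominator, but no visible text does.

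Disposition counts, exposure summaries and full listings would let a reader see that the issue exists. They would not correct the percentages. It is also true that a one-dose rule still leaves some off-drug time in the tables. That is no reason to count patients with no dose at all.

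**Conclusion.** The point holds as a reporting weakness worth fixing. As the SAP is written, patients who stopped blinded drug and stayed in follow-up count in open-label phase safety summaries without any open-label dose.

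The size is uncertain. The number of such patients may be near 0. About 86 is the most the planning figures allow, but it is a planning difference and not a firm bound, and many of those patients may be removed by the existing exclusions. The multipliers from 0.80 to 1.20 also rest on the assumed share f and on assumed event risks in these patients. A reader might take 20% as the expected distortion. The documents do not support that.

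The summaries are descriptive (SAP 2.8). The Week 4 and Week 12 efficacy analyses and the hypotension, hyperkalemia and renal-function incidences through Week 12 are unaffected.

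**What to change.** Keep the calendar phase as a follow-up period and do not delete patients from it. Deletion would lose their medications, deviations and notable laboratory and vital-sign values. Add to SAP 2.1.1 text such as:

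> Open-label phase safety summaries, and any Week 14 or Week 24 column labelled open-label sacubitril/valsartan, will include only patients with at least one open-label dose recorded on any Dosage Administration Record or End of Study Treatment eCRF. Data after the actual or projected Week 12 date for patients without an open-label dose will be presented separately by randomized arm as off-study-treatment follow-up, with use of ACEi, ARB and commercial sacubitril/valsartan shown.

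The flag must not rest on the Visit 7 form alone. SAP 2.1.1 takes the first open-label dose as the one "recorded on the Dosage Administration Record - At Visit (Visit 7) eCRF", and Visit 7 is at Week 14. A patient who started open-label drug and stopped before that visit could be classed as never dosed, and early events after the switch would leave the open-label table.

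The cost is one derived flag, one extra table and a slightly smaller open-label denominator. The data are already collected, and the protocol does not need to change.

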2.2 Analysis sets

The following analysis data sets will be used in the analyses:

Randomized Set (RS): The RS will consist of all randomized patients.

Full Analysis Set (FAS): The FAS will consist of all randomized patients with the exception for those patients who have not been qualified for randomization and have not received study treatment, but have been inadvertently randomized into the study. Following the intent-to-treat principle, patients will be analyzed according to the treatment to which they were assigned at randomization. Efficacy variables will be analyzed based on the FAS as the primary set.

Safety Set (SS): The SS will consist of all randomized patients who have received at least one dose of study treatment. Patients will be included in the analysis according to the treatment actually received. The SS will be used for the analyses of safety variables.

Per-Protocol Set (PPS): The PPS will be a subset of the FAS which will consist of the patients who do not have major deviations from the protocol procedures. Major protocol deviations will be pre-specified prior to unblinding treatment code for analysis. This supplemental efficacy set will be used to support the primary analysis results.

2.2.1 Subgroup of interest

The following subgroups will be analyzed for the primary objective:

1. Age groups (<65, ≥65 years; and <75, ≥75 years)
2. Baseline ejection fraction categories based on echocardiography (<25%, 25% - <35%, ≥35%)
3. Prior ACEi/ARB exposure groups (never exposed, previously exposed, or currently taking)
4. Prior ACEi/ARB dose groups (low dose, high dose) (e.g., low dose: <10 mg enalapril daily [or equivalent]; high dose: ≥10 mg enalapril daily [or equivalent])

5. Baseline quartiles of aortic characteristic impedance (based on FAS)
6. Baseline estimated glomerular filtration rate (eGFR) categories (<45, 45 - <60, ≥60 ml/min/1.73 m²)
7. Groups defined by quintiles of change from baseline in mean arterial pressure at Week 12 (based on FAS)
8. New York Heart Association (NYHA) classification [best value during the past month prior to screening visit] (I, II, III, IV)
9. Prior heart failure hospitalization (No, Yes)
10. Prior diabetes (No, Yes)
11. Baseline plasma NT-proBNP (pg/mL) categories (≤ median, > median) (based on FAS)

See Section 2.5 for further details on the primary objective.

